5.6. General Adverse Events

The occurrence of all treatment-emergent adverse events (excluding infection and ISR), infections, infections considered preventable by vaccination, and injection site reactions will be separately summarized by incidence rate (proportion of subjects reporting events) and adjusted rate per 100 subject-years of exposure to etanercept. Adverse events will also be summarized by severity and relationship to investigational product. Adverse events occurring in >1 subject in any of the subtypes may be summarized as well.

- Tabulations of withdrawals from investigational product due to adverse events will be provided.
- In addition to showing cumulative rates over the entire study period (including both parent study and extension), incidences of subjects with treatment-emergent event as well as exposure-adjusted event rates will also be categorized by year for each year from 1 through 10.

These summaries will be performed for FAS (treatment-emergent events in on-drug period (active and retreatment periods together)) and WAS.

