3.2. Withdrawal Analysis Set

The withdrawal analysis set (WAS) will include those subjects who entered the withdrawal period. Only data collected in the withdrawal period will be included.

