5.5. Malignancies, SAE and Medically Important Infections

The malignancies, serious adverse events and medically important infections will be summarized using the frequency and percentage of subjects reporting events. The adjusted rate per 100 subject-years of exposure to etanercept (defined as # of events/total exposure*100) will be summarized also.

The incidence of malignancies may be compared to external data sources to generate standardized incidence ratios (SIRs) to aid interpretation.

In addition to showing cumulative rates over the entire study period (including both parent study and extension), incidences of subjects with malignancies, serious adverse events and medically important infections as well as exposure-adjusted rates will also be categorized by year for each year from 1 through 10.

These summaries and analyses will be performed for:

- FAS, all events in all periods;
- FAS, treatment-emergent events in the on-drug period (active and retreatment periods together).

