5.11. Exposure

The exposure time (years) to etanercept will be calculated for each subject each period using (the last dose date – the first dose date + 1)/365.25. If the gap is less than 28 days between two etanercept treatment periods, the cumulative exposure will include the gap. Otherwise, the gap will be excluded from the cumulative exposure. Descriptive statistics will be provided to summarize the exposure time for:

- FAS, on-drug period (active and re-treatment periods together);
- FAS, all periods (includes commercial etanercept in withdrawal and observational periods).

The total number of doses of investigational product taken will be summarized for FAS (active and re-treatment periods together).

A table showing the number of subjects taking investigational product for 1 year, 2 years and so on through 10 years may be provided for FAS (active and re-treatment periods together).

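### SAP 5.5 (all periods) and SAP 5.6 (withdrawal set) divide off-drug events by etanercept exposure, and the visible text defines no off-drug or follow-up person-time

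*SAP*

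**What the plan says.** **All-period rates.** SAP 5.5 gives malignancies, SAEs and medically important infections a rate per 100 subject-years of etanercept exposure, "defined as # of events/total exposure*100". One of its two analysis sets is "FAS, all events in all periods"; the other is treatment-emergent events in the on-drug period. Besides cumulative figures, incidences "as well as exposure-adjusted rates will also be categorized by year for each year from 1 through 10".

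**Withdrawal set.** SAP 5.6 summarises general adverse events by "incidence rate (proportion of subjects reporting events) and adjusted rate per 100 subject-years of exposure to etanercept", and its closing sentence applies these summaries both to the on-drug period and to WAS: "These summaries will be performed for FAS (treatment-emergent events in on-drug period (active and retreatment periods together)) and WAS". For WAS, SAP 3.2 states: "Only data collected in the withdrawal period will be included".

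**Person-time.** SAP 5.11 builds exposure from first and last etanercept dose dates. On interruptions it says "If the gap is less than 28 days between two etanercept treatment periods, the cumulative exposure will include the gap"; longer gaps are dropped. It offers two versions: the on-drug period, and "FAS, all periods (includes commercial etanercept in withdrawal and observational periods".

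**What is collected off drug.** Protocol 8.2 has SAEs, malignancy and medically important infections recorded through the observational period, and all adverse events through the withdrawal/re-treatment period. Protocol 5.3.1 prohibits TNF inhibitors other than investigational product in the withdrawal/re-treatment period. It allows any anti-TNF agent, including commercial etanercept, in the observational period.

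**The concern.** A rate needs events and time from the same experience. In the 5.5 all-period analysis, a malignancy or serious infection that starts off etanercept enters the numerator, but the time in which it could have started does not enter the denominator. Malignancy is the primary endpoint, so this reaches the main safety rate of the study.

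The year-by-year display is the more exposed part. If subjects leave etanercept as the years pass, the yearly denominator shrinks while their events still count. A reader could take the resulting rise for a risk that grows with duration, which is the kind of question a ten-year safety follow-up is meant to inform.

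In WAS the difficulty is more basic: a set defined by being off drug has almost no etanercept time to divide by.

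**Working it through.** The plan states no figure on this point, so there is nothing to reproduce. The check sets events against time and then sizes the mismatch.

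**1. Events against time**

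| Planned rate | Events counted | Time counted |
|---|---|---|
| 5.5, on-drug | treatment-emergent | etanercept time: matched, apart from the 30-day tail |
| 5.5, all periods | on and off drug | etanercept time only: not matched |
| 5.6, on-drug | treatment-emergent | etanercept time: matched, apart from the 30-day tail |
| 5.6, WAS | withdrawal period | almost none |

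**2. Size in 5.5.** Let E be events in all periods, T follow-up time and X etanercept time. The planned rate is 100·E/X and the follow-up rate is 100·E/T, so the inflation factor is T/X.

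Inputs: parent study 96 weeks = 672/365.25 = 1.840 years; extension 96 months = 8.0 years (protocol section 3); T = 9.840 years. Let g be the share of extension time off all etanercept, which the documents do not state. Then X = 9.840 − 8g.

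- g = 0: factor 1.00
- g = 25%: 9.840/7.840 = 1.26
- g = 50%: 9.840/5.840 = 1.68
- g = 75%: 9.840/3.840 = 2.56
- g = 100%: 9.840/1.840 = 5.35

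These assume that every subject completes 96 weeks on drug and 96 months of follow-up. Subjects who stopped early in the parent study but were followed on raise the factor. Subjects never enrolled in the extension lower it. Commercial etanercept lowers g, and so the factor, if the all-periods version of exposure is used.

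**3. On the malignancy scale.** Assume 100 subjects (the anticipated enrolment), complete follow-up and one malignancy. Follow-up is 100 × 9.840 = 984 person-years, giving 0.10 per 100 (exact Poisson 95% CI 0.003 to 0.57). With g = 50% the planned denominator is 584 and the rate is 1/584 × 100 = 0.17. With no malignancy both rates are zero.

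**4. A single year.** The factor is 1 divided by the share of that year's follow-up on etanercept: 1.33 at 75%, 2.0 at 50%, 4.0 at 25%. These shares are also assumptions.

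**5. WAS denominator.** A subject who enters withdrawal at baseline and never relapses contributes, beyond day 30 after the last dose, between 8.0 − 30/365.25 = 7.92 and 8.0 − 16/365.25 = 7.96 years (last dose on the baseline day, or 14 days before it), with no etanercept exposure. Only two things could supply a denominator:

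- A bridged gap. This is at most 27 days, 27/365.25 = 0.074 years. It lies wholly inside the 30 days whose events SAP 5.2 and 4.2.2 assign to treatment, so it adds time but no event that WAS may count.
- Commercial etanercept, which SAP 5.11 anticipates although protocol 5.3.1 prohibits it here. As an assumed example, 15 events in 20 subjects over 12 months give 75 per 100 withdrawal person-years. If 5% of that time were on commercial etanercept (1 person-year), the planned rate would be 1500.

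**6. WAS numerator.** SAP 5.6 opens with treatment-emergent events, while SAP 5.2 says that withdrawal onsets more than 30 days after the last dose are not treatment-emergent. SAP 4.2.2 says that such non-serious events are not counted, without saying where. Taken literally, little would remain for the WAS table that 5.6 plans.

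**The case against.** **The rate is labelled and has a matched companion.** SAP 5.5 names its unit as etanercept exposure and also plans an on-drug rate. That stands, and it limits the damage. But a correct label does not make a rate with off-drug events in the numerator interpretable, and no visible passage presents it as a deliberate ever-exposed measure.

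**The two analysis sets in 5.5 mirror the two exposures in 5.11.** On that pairing, all-period events are divided by exposure that includes commercial etanercept. This is a reasonable reading, though 5.5 does not say so. It brings the factor closer to 1, but time off all etanercept is still left out.

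**The large factors are extremes.** This stands. The 5.35 needs every subject off etanercept for all eight years. The protocol's own background (section 1.2) cites a retrospective review in which 69% relapsed after stopping, and relapsing subjects may restart. Nothing in the documents places the study within the range, which begins at 1.0.

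**A programmer would give proportions only for WAS.** Quite likely, but 5.6 asks for the rate.

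**Text not available might settle it.** Protocol 9.4.1 and the SAP text just before 3.2, where the definition of FAS would be expected, are missing from the copy reviewed. SAP 5.1 also leaves analysis intervals to a separate specification. The statement that no other person-time is defined therefore holds for the visible text only.

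**Conclusion.** The point holds. As written, the 5.5 all-period rates are overstated by T/X whenever any follow-up is off all etanercept, and the 5.6 rate in WAS has no usable denominator. The factor is 1.26 to 2.56 if 25% to 75% of extension time is off etanercept, under the completion assumptions above.

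A reader might infer more than the documents support:

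- That the malignancy analysis as a whole is wrong. Counts, percentages and the on-drug rate remain sound.
- That yearly rates will rise. They would do so without a change in risk only if etanercept use falls over time and events occur. With about 100 subjects, malignancies may be few or none.
- That SAP 4.2.2 discards late withdrawal-period events. The sentence is more likely meant to keep them out of the on-treatment count, because the paragraph says it concerns the active and re-treatment periods and SAP 5.2 has a parallel rule. The wording is unclear, and this is a secondary matter.
- That editing the SAP alone is certain to suffice. Protocol section 9 lets the SAP depart from the protocol's plans, but sends major changes to the primary endpoint's analysis to a protocol amendment as well.

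**What to change.** 1. **SAP 5.5.** For all events in all periods, cumulative and by year, divide by total follow-up person-years from first parent-study dose to end of participation (last parent-study contact for subjects never enrolled in the extension). Keep etanercept exposure for the on-drug rates.
2. **SAP 5.11 and 5.6.** Define withdrawal person-time from day 31 after the last dose to the earliest of first re-treatment dose, entry to the observational period, or end of participation. Exclude time on commercial etanercept and list events with onset in that time. Use this as the WAS denominator, with adverse events of onset in the same window and no treatment-emergent filter. Earlier onsets stay in the on-drug table under 5.2 (all events) and 4.2.2 (non-serious events).
3. **SAP 4.2.2.** Reword the last sentence of the non-serious adverse event paragraph to say that such an event is not counted in the active or re-treatment period.

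The cost is a few wording edits and two derived denominators from dates already collected, with no new data. Protocol 9.4.2 carries the same etanercept-exposure wording for the withdrawal/re-treatment period; protocol section 9 lets the SAP modify it. Because edit 1 changes the denominator of the primary endpoint's rate, the sponsor should check it against protocol 9.4.1 and decide whether it is a major modification that calls for an amendment.

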9.2. Efficacy Analysis

9.2.1. Analysis of Primary Endpoint

The primary endpoint in this study are related to safety. Efficacy endpoints are secondary.

9.2.2. Analysis of Secondary Endpoints for Subjects in the Active Treatment Period, and Withdrawal/Re-treatment Period

The secondary efficacy endpoints will be analyzed in the active treatment period and the withdrawal/re-treatment period. For the overall population as well as each of the JIA subpopulations, descriptive statistics will be provided for each study endpoint at all time points in the study. For categorical endpoints, the summary statistics will contain the frequency, percentage, and 95% confidence interval (CI) for the percentage. For continuous endpoints, the summary statistics will contain the number of observations, mean, standard

9.4.2. Safety Analysis for Subjects in the Active Treatment Period, and Withdrawal/re-treatment Period:

The occurrence of all adverse events (infectious and noninfectious), infections considered preventable by vaccination, and injection site reactions as well as treatment-emergent adverse events, potentially clinically important laboratory measurements, and premature discontinuations during the study will be summarized as using frequency and percentage, as well as adjusted rate per 100 subject-years of exposure to etanercept.

For laboratory data, vital sign measurements, and other continuous safety data, the number of observations, mean, standard deviation, median, minimum, maximum, and 95% CI of the mean will be summarized by visit for raw data and the change from baseline. Height, weight, BMI, and Tanner scores will be summarized using the number of observations, mean, standard deviation, median, minimum, and maximum by age group. Height, weight and BMI will also be compared with data from standardized growth charts.

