3.3. Re-treatment Analysis Set

The re-treatment analysis set (RTAS) will include those subjects who entered the re-treatment period. Only data collected in the re-treatment period will be included.

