5.2. Treatment-emergent Events

An event is defined as a treatment-emergent event if the event occurred during the active period (either parent or extension studies) or re-treatment period with onset dates between the first dose date of investigational product and within 30 days after the last dose of investigational product. If a treatment-emergent event started in active or re-treatment period and continued to withdrawal or observational period, it will be only counted in active or re-treatment period, it will not be counted in withdrawal or observational period again. If an event started in the withdrawal or observational periods, and after 30 days of the last dose of investigational product of the active period or re-treatment period, this event is not a treatment-emergent event.

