5.7. Laboratory, Vital Signs, Tanner Stage Assessment

For laboratory data, vital sign measurements and other continuous safety data, the number of observations, mean, standard deviation, median, minimum, maximum will be summarized by visit. Height, weight, BMI, and Tanner scores will be summarized using the number of observations, mean, standard deviation, median, minimum, and maximum by age group (ages 2-4, 5-11 and 12-17 years at start of parent study). The visits shown in these reports will be the baseline visit from the parent study, weeks 12, 24, 48, and 96, from the parent study and all visits from the extension study where

the data is collected. Some additional analyses of the Tanner data that takes age at time of measurement into account may also be done.

The Potentially Clinically Important (PCI) Flag is a derived flag value based on the PCI criteria defined for laboratory data captured in the study. The PCI criteria are based on NCI toxicity criteria. The number (%) of subjects with PCI events will also be provided for the lab data.

These summaries will be performed for FAS (active period (both parent and extension studies)), WAS, and RTAS.

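### Adverse-event tables show re-treatment only pooled with first-course etanercept, although a re-treatment analysis set exists and is used for most other data

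*SAP*

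**What the plan says.** SAP 3.3 defines the set: "The re-treatment analysis set (RTAS) will include those subjects who entered the re-treatment period". It is restricted to data from that period.

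The set is then used unevenly.

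- **Used:** SAP 5.4 (baseline), 5.7 (laboratory values with potentially clinically important [PCI] flags, vital signs, Tanner), 5.8 (growth) and 5.9 (efficacy). SAP 5.7 is typical: "These summaries will be performed for FAS (active period (both parent and extension studies)), WAS, and RTAS".
- **Not used:** SAP 5.6 names only the pooled on-drug period and the withdrawal set (WAS): "These summaries will be performed for FAS (treatment-emergent events in on-drug period (active and retreatment periods together)) and WAS". SAP 5.5 names all periods together, and "FAS, treatment-emergent events in the on-drug period (active and retreatment periods together".

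The supporting definitions follow the pooling. Under SAP 5.2 an event is treatment-emergent if "the event occurred during the active period (either parent or extension studies) or re-treatment period", with a window running to 30 days after the last dose. SAP 5.11 summarises exposure for "FAS, on-drug period (active and re-treatment periods together".

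On the protocol side, 2.2.3 lists these safety endpoints for subjects in the active and the withdrawal/re-treatment periods. Section 9.4.2 is headed "Safety Analysis for Subjects in the Active Treatment Period, and Withdrawal/re-treatment Period" and calls for frequency, percentage and a rate per 100 subject-years.

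**The concern.** The withdrawal/re-treatment period was added because little was known about when to stop etanercept and how well restarting works after relapse. Long-term safety is a secondary objective. A reader of the report would want the adverse-event experience after restart, particularly infections and injection site reactions, next to the efficacy after restart. The SAP supplies the second but not the first. The off-drug withdrawal period gets its own adverse-event table, while the period in which drug is resumed does not, and no reason is stated. If rates after a break differ from first-course rates, pooling pulls the displayed figure towards the first-course rate in proportion to how little re-treatment time there is.

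**Working it through.** The plan gives no figure to reproduce: enrolment of about 100 does not come from a calculation, and neither the number re-treated nor their time on drug is stated.

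**Step 1. Is there a re-treatment-only adverse-event table anywhere?** Going through the visible SAP analysis sections, RTAS appears in 5.4, 5.7, 5.8 and 5.9. It is absent from 5.5, 5.6 and 5.11. SAP 5.13 and 5.14 list hospitalised subjects and deaths for the FAS.

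**Step 2. Do the by-year tables separate it?** SAP 5.6 says "exposure-adjusted event rates will also be categorized by year for each year from 1 through 10", and SAP 5.5 does the same. These run on the same pooled populations. Subjects can enter withdrawal at extension baseline or later from the active period, so restarts fall in different years and mix with first-course exposure still running in those years.

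**Step 3. How much does pooling dilute?** Let f be re-treatment person-years divided by all on-drug person-years, and RR the event rate on re-treatment relative to the first course. Then

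pooled rate / first-course rate = (1 − f) + f × RR = 1 + f(RR − 1).

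Inputs from the documents: about 100 subjects; about 96 weeks in the parent study (96 × 7 / 365.25 = 1.84 years); up to 96 further months; one withdrawal/re-treatment cycle per subject. Assumptions: a mean of 2 or 4 further first-course years, giving 100 × (1.84 + 2) = 384 or 100 × (1.84 + 4) = 584 person-years; 5 to 30 subjects re-treated for 1 to 4 years each.

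| Case (assumed) | First course | Re-treatment | f | RR 2 | RR 3 | RR 5 |
|---|---|---|---|---|---|---|
| Low | 584 | 5 × 1 = 5 | 5/589 = 0.8% | 1.01 | 1.02 | 1.03 |
| Middle | 384 | 15 × 2 = 30 | 30/414 = 7.2% | 1.07 | 1.14 | 1.29 |
| High | 384 | 30 × 4 = 120 | 120/504 = 23.8% | 1.24 | 1.48 | 1.95 |

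The last three columns are pooled ratios; exposure is in person-years.

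**Step 4. What would a separate column show?** Take 30 re-treatment person-years, an assumed first-course rate of 5 per 100 and RR 3. Expected events are 30 × 0.15 = 4.5. Observing 4 gives 13.3 per 100 person-years, with an exact Poisson 95% interval of 3.6 to 34.1.

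**Step 5. Does the rate's denominator fit its numerator?** SAP 5.2 counts events to 30 days after the last dose; exposure in SAP 5.11 stops at the last dose. With a constant event rate, the uncounted tail inflates the rate by 30 divided by the course length in days: 30 / 182.6 = about 16% for a 6-month course, and 30 / 1461 = about 2% for a 4-year course. A split that kept these definitions would make a short re-treatment course look worse than a long first course with no true difference.

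**The case against.** There is a good case that this is a matter of presentation. Every treatment-emergent re-treatment event is counted in the on-drug tables. Events and doses are dated, so a separate table could be made later. PCI laboratory events, vital signs and growth are already shown for RTAS, deaths and hospitalisations are listed, and the Internal Review Committee monitors safety throughout. The amendment's stated aim, in the SAP introduction, is to explore clinical benefit and physical function, not a safety contrast on re-exposure. A re-treatment column would be imprecise (step 4), and any comparison with the first course is confounded by age, calendar time and the selection of subjects who relapsed.

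Most of this stands, and it limits what may be claimed. A reader might infer that the SAP breaks a protocol commitment. It does not: Protocol 2.2.3 and 9.4.2 name the endpoints and the subjects covered but do not promise results by period. A reader might also infer that an excess on restart would vanish, or be indistinguishable from chance. The documents do not support that either. In the high case above a fivefold excess nearly doubles the pooled rate, and no event counts are available from which to judge noise.

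The objection does not explain why RTAS is good enough for efficacy and laboratory data but left out of the adverse-event tables. Small numbers affect both alike.

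**Conclusion.** The gap is real but limited to adverse-event-type tables: treatment-emergent events, infections, injection site reactions, withdrawals due to adverse events, serious events, malignancies and medically important infections. For these, the visible SAP text never shows re-treatment on its own.

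The direction of the dilution follows from the arithmetic. Its size does not, because f is unknown; the range of 1.02 to 1.48 for a tripling rests wholly on the assumed exposure in step 3. The conclusion is also confined to the text that can be read: the FAS definition, the body of Protocol 9.4.1 and some redacted text were not available.

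Splitting the tables would describe safety after restart. It should not be expected to settle whether events are more frequent on re-exposure. It is worth doing because it is cheap and puts the safety of restarting beside its efficacy.

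**What to change.** 1. In SAP 5.5 and 5.6, present on-drug events in three columns: active period (parent plus extension), re-treatment period (RTAS), and combined.
2. Add the same three-way split to the exposure summary in SAP 5.11.
3. Match person-time to the event window in both period columns: either add the 30-day tail to the denominator, or restrict the rate numerator to events up to the last dose.
4. State how events and time are assigned when drug is restarted within the 30-day window, or when the gap is short enough for SAP 5.11 to count it as exposure, so that the two columns add up to the combined one.
5. Label the RTAS results descriptive and imprecise, and note the confounding by age, calendar time and relapse selection beside any comparison with the first course.

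The cost is SAP wording and extra columns in tables already planned. No new data are needed, since SAP 5.11 already calculates exposure by subject and period and the treatment-emergent definition already covers re-treatment.
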